2.3.2 Known Potential Benefits

Since the patients included in this protocol have metabolic abnormalities, they have some likelihood of clinical benefit from this trial. Patients have abnormalities causing a severe state of insulin resistance and often diabetes. Improvements in the patients' insulin sensitivity also have repercussions in improving patients' risks for diabetes. If patients have already had diabetes, improvements in insulin sensitivity can improve their diabetes control, and thus potentially reduce secondary complications normally seen in patients with Type 2 diabetes (heart disease, retinopathy, kidney disease).

Furthermore, the collected data may be used to answer some relevant clinical and basic questions involved in the disease processes. Therefore, there is a chance that future patients may also benefit from the results of this study.

2.3.3 Assessment of Potential Risks and Benefits

Our 20 year experience with metreleptin in patients with mutations of the insulin receptor and lipodystrophy shows that the risk profile of this drug is generally mild and manageable. Patients with mutations of the insulin receptor who are treated in this study have the potential for benefit from improved diabetes control, leading to lower risk of blindness, kidney failure, and amputation.

Abbreviated Title: Effects of leptin in insulin resistance
Version Date: AM N ver. (approved 10/21/20); rev for AM O (5/5/21)

3 OBJECTIVES AND ENDPOINTS

OBJECTIVES	ENDPOINTS	JUSTIFICATION FOR ENDPOINTS
Primary		
To determine if metreleptin will improve glycemia control in patients with genetic defects of the insulin receptor.	Hemoglobin A1c	Hemoglobin A1c is a standard measure of efficacy of diabetes interventions, which correlates with risk of microvascular complications of diabetes.
Secondary		
To determine mechanisms by which metreleptin improves glycemia.	Fasting glucose, insulin, and C-peptide; glucose, insulin, and C-peptide area under the curve after oral glucose tolerance testing (OGTT)	Fasting and post-OGTT glucose, insulin, and C-peptide provide additional measures of glycemia, beta-cell function, and insulin resistance.
Tertiary		
To determine mechanisms by which leptin signals starvation and nutrient repletion	Body weight, body composition, creatinine clearance, urine 24-hour protein, hypothalamic pituitary function	These endpoints will offer insight into mechanisms by which leptin affects appetite and hormonal signals of starvation and nutrient repletion.

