4 STUDY DESIGN

4.1 OVERALL DESIGN

This study is designed to investigate the effect of recombinant leptin on various metabolic and hormonal abnormalities in patients with known or suspected mutations of the insulin receptor gene. These patients have low leptin levels in addition to other metabolic abnormalities. This study utilizes an open-label design, and the accrual ceiling is set at 20 patients. Cumulative changes in each patient will be compared to his/her baseline state after 6 and 12 months. The primary outcome will be assessed after 12 months of study drug. After the patient has completed one year of therapy and has shown metabolic improvement on the medication and the patient desires to continue therapy, the PI at NIH will consider extending therapy on an annual basis. The study medication is supplied through Amryt Pharma, and neither NIH nor Amryt Pharma can guarantee its availability after the study ends.

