4.2 SCIENTIFIC RATIONALE FOR STUDY DESIGN

Given the extreme rarity of mutations of the insulin receptor, a placebo-controlled study is not feasible. Hence, an open-label within subjects design has been chosen.

Abbreviated Title: Effects of leptin in insulin resistance

Version Date: AM N ver. (approved 10/21/20); rev for AM O (5/5/21)

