5 STUDY POPULATION

5.1 INCLUSION CRITERIA

In order to be eligible to participate in this study, an individual must meet all of the following criteria:

1. Provision of signed and dated informed consent form
2. Male or female, aged ≥ 5 years.
3. Clinically significant, severe insulin resistance caused by a known or suspected defect in the insulin receptor.
4. Presence of at least one of the following metabolic abnormalities:
 - a) Fasting insulin $>30 \mu\text{U}/\text{ml}$, or
 - b) Presence of diabetes as defined by the 2006 ADA criteria:
 - i. Fasting plasma glucose $\geq 126 \text{ mg/dL}$
 - ii. 2 hour plasma glucose $\geq 200 \text{ mg/dL}$ following a 75 gram (1.75g/kg if less than 40kg) oral glucose load, or
 - iii. Diabetic symptoms with a random plasma glucose $\geq 200 \text{ mg/dL}$
5. Ability of subject Legally Authorized Representative (LAR) to understand and the willingness to sign a written informed consent document.

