5.3 INCLUSION OF VULNERABLE PARTICIPANTS

Children: Patients with mutations of the insulin receptor, particularly those with biallelic mutations causing Rabson Mendenhall Syndrome, typically develop diabetes in childhood, with death often occurring in the second or third decade of life. Because this is a pediatric condition, most patients enrolled in this study will be <18 years of age. Children <5 years of age may not enroll. In our experience with the younger children, we find that their participation in serial blood tests improves greatly when they are at least 5 years of age. Also, in our experience with the patients with mutations of the insulin receptor, their initial insulin resistance is manifested as

Abbreviated Title: Effects of leptin in insulin resistance

Version Date: AM N ver. (approved 10/21/20); rev for AM O (5/5/21)

extreme hyperinsulinemia and hypoglycemia (rather than hyperglycemia) in the younger patients. We would not want to treat a young child experiencing chronic hypoglycemia.

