9 STATISTICAL CONSIDERATIONS

9.1 STATISTICAL HYPOTHESIS

- Primary Endpoint(s): The primary outcome measure is improvement in HbA1c after 1 year of metreleptin,
- Secondary Endpoint(s): A number of secondary endpoints will also be studied. These include fasting blood glucose, and insulin, and C-peptide levels, as well as the glucose, insulin, and C-peptide responses to glucose tolerance tests. In the pilot study, we have observed up to a 40% reduction in fasting blood glucose, and an even greater reduction in endogenous hyperinsulinemia. While we would hope to see changes of this magnitude we cannot pre-define the extent of improvement or lack thereof that may occur.
- Exploratory Endpoints: These include body weight, body composition, creatinine clearance, and urine 24-hour protein. In addition, we will include hypothalamic pituitary parameters, LH/FSH, and thyroid function.

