9.4 STATISTICAL ANALYSES

9.4.1 General Approach

The patients are all analyzed as a function of their baseline metabolic status. Each patient is his/her own control against their own baseline data. The appropriate statistical analysis as applied in our study of lipodystrophic patients will be utilized. Under certain conditions student's t-test and ANOVA will be used. Under circumstances of data that is not distributed normally, log-transformations will be carried out.

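### No growth adjustment is stated for the exploratory weight and renal endpoints, so in participants who are still growing, change from baseline mixes growth with drug effect

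*Combined protocol and SAP*

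**What the plan says.** - **Endpoints.** The tertiary row of the Section 3 table lists "Body weight, body composition, creatinine clearance, urine 24-hour protein, hypothalamic pituitary function". The objective they serve is "To determine mechanisms by which leptin signals starvation and nutrient repletion". Section 9.1 calls them exploratory: "These include body weight, body composition, creatinine clearance, and urine 24-hour protein". Neither place mentions a z-score, a percentile or indexing to body size.
- **Comparison.** Section 4.1: "Cumulative changes in each patient will be compared to his/her baseline state after 6 and 12 months". Section 9.4.1: "Each patient is his/her own control against their own baseline data". Section 4.2 explains that a placebo control is not feasible, so "an open-label within subjects design has been chosen".
- **Population.** Section 5.1 admits "Male or female, aged ≥ 5 years" and sets no upper limit. Section 5.3 expects that "most patients enrolled in this study will be <18 years of age".
- **Expected effect on weight.** Section 2.3.1 describes weight loss as frequent on metreleptin, especially at the high doses of this study. It gives no size. No direction is given for creatinine clearance or urine protein.
- **Analysis.** Section 9.4.1 names t-tests, ANOVA and log-transformation, and otherwise defers to the analysis used in an earlier lipodystrophy study. Section 9.4.7 plans no sub-groups. Section 9.4.9 (exploratory analyses) gives no method.
- **Data available.** Height and weight are scheduled at every visit (Section 1.3). Section 8.2.1 adds BMI, cystatin C and a pubertal examination where age-appropriate.

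**The concern.** A single-arm before-after comparison credits any time trend to the drug. HbA1c does not rise merely because a child gets bigger, so using each patient as his or her own control is more defensible for the primary endpoint. Weight does rise with growth, and 24-hour renal output may rise with body size. The plan states one general approach and makes no distinction between these kinds of variable.

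For weight, growth and the expected drug effect pull in opposite directions. A real loss relative to expected growth could be reported as little or no change. With no drug effect at all, ordinary growth could be reported as a gain and read as nutrient repletion, which is the subject of the tertiary objective.

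**Working it through.** **The plan's own figures.** There is no sample size, effect size or SD for these endpoints. The only calculation, in Section 9.2, concerns HbA1c. It is reproduced by a paired two-sided t-test at 0.05 (noncentral t): change 2.1, SD 1.4, n = 6 gives 83.3% power; change 2.0, SD 1.5, n = 7 gives 83.4%. The present point does not touch it.

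Everything below is assumption, shown as a range.

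**Step 1: weight in one child.** Let W be baseline weight, g the growth over the year without drug, and e the true drug-related loss relative to the weight growth alone would have given.

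Observed change = (1 + g/W)(1 - e) - 1. The observed change is zero when e = g/(W + g).

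With W = 30 kg:

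| Growth in 12 months | True 5% loss seen as | True 10% loss seen as | Loss exactly cancelled |
|---|---|---|---|
| 0 kg | -5.0% | -10.0% | 0% |
| 1 kg | -1.8% | -7.0% | 1/31 = 3.2% |
| 2 kg | +1.3% | -4.0% | 2/32 = 6.25% |
| 3 kg | +4.5% | -1.0% | 3/33 = 9.1% |
| 4 kg | +7.7% | +2.0% | 4/34 = 11.8% |
| 6 kg | +14.0% | +8.0% | 6/36 = 16.7% |

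For example, at 3 kg: 1.10 x 0.90 - 1 = -1.0%. The result runs from no bias, through attenuation, to reversal. The sign changes only when growth exceeds the drug effect.

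At 6 months less growth has accrued. If 1.5 kg has been gained and the full 10% loss already reached, the observed change is 1.05 x 0.90 - 1 = -5.5%.

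**Step 2: the group comparison.** Assume n = 20 (the accrual ceiling), a true mean drug effect of -2 kg, and a paired two-sided t-test at 0.05. Mean growth is averaged over all patients, growing or not.

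| Mean growth | Chance of detecting a loss, SD 2 kg | Same, SD 3 kg | Chance of a significant gain with no drug effect, SD 2 kg | Same, SD 3 kg |
|---|---|---|---|---|
| 0 kg | 99% | 81% | 2.5% (nominal) | 2.5% (nominal) |
| 0.5 kg | 89% | 56% | 18% | 11% |
| 1 kg | 56% | 29% | 56% | 29% |
| 1.5 kg | 18% | 11% | 89% | 56% |
| 3 kg | 0% | 0% | about 100% | 99% |

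**Step 3: renal measures.** Assume output scales with body surface area (BSA), with BSA = sqrt(height x weight / 3600), for a child of 135 cm and 30 kg.

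- Growth of 2 cm and 1 kg: sqrt(137 x 31 / (135 x 30)) - 1 = +2.4%.
- Growth of 8 cm and 6 kg: sqrt(143 x 36 / (135 x 30)) - 1 = +12.7%.
- A true 10% fall in the indexed value is then seen unindexed as 1.024 x 0.90 - 1 = -7.8% to 1.127 x 0.90 - 1 = +1.5%.
- A true 10% rise is seen as 1.024 x 1.10 - 1 = +12.6% to 1.127 x 1.10 - 1 = +24.0%.

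So growth masks a fall and exaggerates a rise.

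**The case against.** **The sizes are all assumed.** This stands. The documents give no growth rate, drug effect or SD for these endpoints. The patients have a paucity of fat and limited longevity (Section 2.2), so normal growth may not apply to them. Under 18 does not mean still growing, adults are eligible, and the ages of the 11 enrolled patients are not given. A reader might infer that growth will hide or reverse the drug effect. The documents support only that it can.

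**The renal measures may be affected differently.** This also stands. A reader might carry the masking argument over from weight, but with no stated drug direction only confounding is supported.

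**Raw and unindexed values are inferred from silence.** Partly stands. Section 8.2.1 gives no units for creatinine clearance, so indexed reporting is not excluded. The earlier lipodystrophy analysis to which Section 9.4.1 defers might standardise weight, and cannot be checked here. But weight itself is the named endpoint, own baseline is the stated comparator, and nothing in the text reviewed adjusts for growth.

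**The consequence is small.** Stands as to severity. These are tertiary or exploratory endpoints in at most 20 patients, with no stated hypothesis test. Section 9.4.8 allows individual listings, where height and weight can be read together, but that is optional and is not an analysis. A reader might also infer a gap in safety monitoring. Weight monitoring for safety is separate (Sections 2.3.1 and 6.1.2.3), and this point makes no claim about it.

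**Conclusion.** The point holds in limited form and is a minor one. For weight, the confounding follows from the protocol's own statements (single arm, own baseline, mostly minors, expected weight loss) together with the fact that children grow. The direction is upward in anyone still growing. Its size is unknown: for a 30 kg child with a true 10% loss and 0 to 4 kg of growth, the observed change ranges from -10% to +2%. For creatinine clearance and 24-hour protein, the supported conclusion is confounding by body size, conditional on the values not already being indexed. The HbA1c analysis and the sample size stand as they are. What changes is what the tertiary objective can conclude in growing participants.

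**What to change.** Add to Section 9.4, for the tertiary endpoints:

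- For participants under 18 (by age at baseline), analyse change in age- and sex-standardised weight and BMI z-scores from a named growth reference. For adults, use raw weight.
- Report creatinine clearance and 24-hour urine protein indexed to body surface area, or state that the laboratory values already are.
- Show minors and adults separately, descriptively, since numbers are small.

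A z-score removes the growth expected in the reference population. It does not remove any departure from that growth caused by the disease itself, so the limits of a single-arm comparison should still be stated.

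The cost is a few lines of analysis text and a routine calculation from age, sex, height and weight. No new visits, samples or patients are needed, and no clinical management changes.

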4 STUDY DESIGN

4.1 OVERALL DESIGN

This study is designed to investigate the effect of recombinant leptin on various metabolic and hormonal abnormalities in patients with known or suspected mutations of the insulin receptor gene. These patients have low leptin levels in addition to other metabolic abnormalities. This study utilizes an open-label design, and the accrual ceiling is set at 20 patients. Cumulative changes in each patient will be compared to his/her baseline state after 6 and 12 months. The primary outcome will be assessed after 12 months of study drug. After the patient has completed one year of therapy and has shown metabolic improvement on the medication and the patient desires to continue therapy, the PI at NIH will consider extending therapy on an annual basis. The study medication is supplied through Amryt Pharma, and neither NIH nor Amryt Pharma can guarantee its availability after the study ends.

4.2 SCIENTIFIC RATIONALE FOR STUDY DESIGN

Given the extreme rarity of mutations of the insulin receptor, a placebo-controlled study is not feasible. Hence, an open-label within subjects design has been chosen.

Abbreviated Title: Effects of leptin in insulin resistance

Version Date: AM N ver. (approved 10/21/20); rev for AM O (5/5/21)

4.3 JUSTIFICATION FOR DOSE

Subjects will be begin at a determined efficacious dose for this group of patients of 0.2 mg/kg/day for both female and male subjects.

5 STUDY POPULATION

5.1 INCLUSION CRITERIA

In order to be eligible to participate in this study, an individual must meet all of the following criteria:

1. Provision of signed and dated informed consent form
2. Male or female, aged ≥ 5 years.
3. Clinically significant, severe insulin resistance caused by a known or suspected defect in the insulin receptor.
4. Presence of at least one of the following metabolic abnormalities:
 - a) Fasting insulin $>30 \mu\text{U}/\text{ml}$, or
 - b) Presence of diabetes as defined by the 2006 ADA criteria:
 - i. Fasting plasma glucose $\geq 126 \text{ mg/dL}$
 - ii. 2 hour plasma glucose $\geq 200 \text{ mg/dL}$ following a 75 gram (1.75g/kg if less than 40kg) oral glucose load, or
 - iii. Diabetic symptoms with a random plasma glucose $\geq 200 \text{ mg/dL}$
5. Ability of subject Legally Authorized Representative (LAR) to understand and the willingness to sign a written informed consent document.

5.2 EXCLUSION CRITERIA

An individual who meets any of the following criteria will be excluded from participation in this study:

1. Pregnant at time of enrollment, women in their reproductive years who do not use an effective method of birth control, and women currently nursing or lactating within 6 weeks of having completed nursing.
2. Known infectious liver disease
3. Known HIV infection
4. Current alcohol or substance abuse
5. Active tuberculosis
6. Use of anorexiogenic drugs
7. Other conditions which in the opinion of the clinical investigators would impede completion of the study.
8. Subjects who have a known hypersensitivity to E. Coli derived proteins.

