2.3 RISK/BENEFIT ASSESSMENT

2.3.1 Known Potential Risks

Risks of Metreleptin:

Metreleptin was FDA-approved to treat the complications of leptin deficiency in patients with congenital and acquired lipodystrophy in 2014. Potential risks of metreleptin based on studies in patients with generalized and partial lipodystrophy, obesity, and other populations are summarized in the Prescribing Information (<http://www.myalept.com/prescribing-information>).

Key potential side effects are summarized below:

1. Injection site reactions: The most frequently reported adverse events in studies of metreleptin have been skin reactions (injection site reactions) at the site where the drug is injected. injection site reactions of erythema, pruritus, inflammation (induration), urticaria and edema were reported in 40% of subjects from the previous studies (compared to 15% of placebo-treated subjects) (Investigator's Brochure). The majority were reported as mild in severity with average time of onset of 15 days. All sites of injection (abdomen, arm and leg) used for the site of injection were affected. Higher doses appeared to have greater incidence and earlier onset (Investigator's Brochure). Biopsies of the injection site have been reported in the Investigator's brochure from 2 cases. The results were similar and consistent with a delayed hypersensitivity reaction to the protein (Investigator's Brochure).

Mild to moderate injection site ecchymosis was reported in 56% of all subjects, with a higher incidence occurring with subcutaneous bolus administration (as planned in this study) as opposed to administration with continuous infusion. There were no reported systemic symptoms to suggest a systemic allergic reaction. Some of the local reactions have been moderated with antihistamines, anti-inflammatory agents, topical steroids and cold compresses. In some subjects, investigators have reported gradual decreases in severity over time to complete disappearance of injection site reactions during continuous study-drug administration (Investigator's Brochure).

2. Hypersensitivity: Hypersensitivity reactions (e.g. anaphylaxis, urticaria, generalized rash) have been observed. Subjects who have a known history of anaphylaxis or anaphylactic-like reactions should not be administered Metreleptin. Also, subjects who have a known hypersensitivity to E. Coli derived proteins should not be administered Metreleptin because the Metreleptin protein is expressed in an E. Coli system.

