7.2 PARTICIPANT DISCONTINUATION/WITHDRAWAL FROM THE STUDY

Participants are free to withdraw from participation in the study at any time upon request.

An investigator may discontinue or withdraw a participant from the study for the following reasons:

- Adverse events that are not readily explained by other causes unrelated to current protocol. Examples include:
 - Systemic life-threatening allergic reaction to metreleptin
 - Other significant medical issues that will, in the judgment of the investigators, preclude safe completion of the study.
- Noncompliance with self-monitoring requirements and Clinical Center visits
- Development of any medical problem listed in the exclusion criteria
- Significant medical issues that will in the judgment of the investigators preclude safe completion of the study. If an investigator feels it is in the subject's best interest to terminate participation, the detailed reasoning behind this decision will be documented. Examples include change in benefit-risk ratio of metreleptin treatment for an individual patient, such as:
 - Loss of efficacy of metreleptin (e.g. due to development of neutralizing antibodies)
 - Development of a medical condition that might increase risks associated with metreleptin (e.g. T-cell lymphoma, high risk thyroid cancer) in a patient not receiving dramatic clinical benefit
 - More than 8% drop in hematocrit and discontinuation recommended by Hematology Service
 - WBC count < 2500 or absolute neutrophil count < 1000 and discontinuation recommended by Hematology Service
- Death

The reason for participant discontinuation or withdrawal from the study will be recorded in the medical record.

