10.9.1 NIH Definition of Protocol Deviation

A protocol deviation is any changed, divergence, or departure from the IRB-approved research protocol.

- **Major deviations:** Deviations from the IRB approved protocol that have, or may have the potential to, negatively impact the rights, welfare or safety of the subject, or to substantially negatively impact the scientific integrity or validity of the study.
- **Minor deviations:** Deviations that do not have the potential to negatively impact the rights, safety or welfare of subjects or others, or the scientific integrity or validity of the study.

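### Section 2.3.1 says two groups should not be given metreleptin, but the 5.2 exclusion list carries over only one; a history of anaphylaxis is missing from eligibility

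*Combined protocol and SAP*

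**What the plan says.** Section 2.3.1 (Known Potential Risks), item 2, reports that "Hypersensitivity reactions (e.g. anaphylaxis, urticaria, generalized rash) have been observed". It then gives two restrictions in succession. The first is "Subjects who have a known history of anaphylaxis or anaphylactic-like reactions should not be administered Metreleptin". The second is "Also, subjects who have a known hypersensitivity to E. Coli derived proteins should not be administered Metreleptin", with the reason that the drug is made in an E. coli expression system.

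Section 5.2 opens its list with "An individual who meets any of the following criteria will be excluded from participation in this study" and numbers eight items. Item 8 is "Subjects who have a known hypersensitivity to E. Coli derived proteins". Item 7 is a general clause: "Other conditions which in the opinion of the clinical investigators would impede completion of the study". None of the eight mentions anaphylaxis or an anaphylactic-like reaction.

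**The concern.** Both restrictions in 2.3.1 are worded as bars on giving the drug, and the second opens with a word that marks it as an addition to the first. One would expect both to appear in the list that decides who may enter. Only one does, in almost the same words as 2.3.1, and nothing in the protocol explains why its companion was left out. An oversight is the natural inference, although the text does not prove it.

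What is at stake is safety at entry. Eligibility is the step at which exposure can be prevented. Here the investigator would have one section under which a patient qualifies and another under which the same patient should not be treated.

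**Working it through.** No figure in the plan bears on this, so the check is a comparison of texts.

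**Step 1. Groups restricted in 2.3.1, item 2.**
- Group A: known past anaphylaxis or anaphylactic-like reaction.
- Group B: known hypersensitivity to E. coli proteins.

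**Step 2. Where each group appears among the rules that control entry and continuation.**

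| Section | Group A | Group B |
|---|---|---|
| 5.1 Inclusion criteria (items 1 to 5) | not mentioned | not mentioned |
| 5.2 Exclusion criteria, items 1 to 6 | not mentioned | not mentioned |
| 5.2, item 7 | not named; exclusion possible by judgement | not named; exclusion possible by judgement |
| 5.2, item 8 | not mentioned | named |
| 8.1.1 Pre-consent screening | record review, contents not itemised for allergy | same |
| 8.1.2 Post-consent screening | leptin level only | leptin level only |
| 7.2 Discontinuation | not named | reached only through the reference back to 5.2 |

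One of the two restricted groups reaches the exclusion list.

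**Step 3. Does another provision supply Group A?**
- Item 7 of 5.2 rests on investigator opinion and asks whether a condition would stop the patient finishing the study. The test in 2.3.1 is whether the patient should be dosed at all.
- The allergy example in 7.2 is a life-threatening systemic reaction to metreleptin itself, so it operates after exposure.
- The 7.2 rule on developing a condition from the exclusion list points back to 5.2 and so inherits the omission.
- Section 10.9.1 counts any "departure from the IRB-approved research protocol" as a deviation. Dosing a Group A patient could be classed that way because 2.3.1 is protocol text. That confirms the conflict and does not remove it.

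**Step 4. How many patients could be affected.** The accrual ceiling is 20 (section 4.1) and 11 are enrolled (section 5.6). Further enrolments are at most 20 − 11 = 9. The documents give no prevalence of past anaphylaxis in this population, so the expected number among those 9 cannot be derived from them.

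**The case against.** The strongest reply is that the protocol, read as a whole, already keeps these patients out. The study consists of taking one drug for 12 months. A patient who should not receive that drug cannot complete it, so an investigator who reads 2.3.1 together with item 7 would exclude. Screening also gives real opportunities to find the history: existing records may be reviewed before consent (8.1.1), some recruits come from a cohort already followed under an NIH natural history protocol (5.6), a history is taken on admission and injections start in hospital (1.3), and the team meets to discuss potential patients (10.7). The protocol does not itemise the contents of any history, so its silence on allergy is weak evidence that nobody asks.

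Much of this stands, and it keeps the point small. It does not close the gap. Item 7 permits exclusion without requiring it, and it applies a different test. None of the screening steps says that past anaphylaxis must be checked.

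A second reply concerns scope. The sentence in 2.3.1 names no trigger. Read literally, it covers anaphylaxis from any cause. Its place beside the E. coli rationale also allows a reading limited to metreleptin or its components, in which case item 8 already covers much of it. That is fair, and it affects which wording is right. On either reading the two sections should agree.

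A third reply is that the safety weight is modest. Section 2.3.1 gives anaphylaxis as one example of observed reactions, with no rate. Its item on injection-site reactions says no systemic symptoms suggesting allergy were reported there, and 2.3.3 describes the risk profile as generally mild and manageable. This too is accepted.

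**Conclusion.** The mismatch is certain on the text: two groups are restricted in 2.3.1 and one of them is excluded in 5.2. It is a minor internal inconsistency with a bearing on safety. It reaches at most 9 future enrolments, plus any current participant who has such a history. No endpoint, sample size or analysis is touched.

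A reader might infer more, and the documents do not support it:
- **That the protocol lacks the restriction, or deliberately admits these patients.** The restriction stands in 2.3.1, and item 7 allows it to be applied. It is only missing from the list that makes exclusion mandatory.
- **That patients have been, or are likely to be, harmed.** Nothing shows that anyone enrolled has such a history. With no prevalence and no reaction rate given, neither the number of affected patients nor the number of reactions can be estimated.
- **That this is a disputed design choice.** No rationale for treating the two groups differently is offered, so there is no choice to argue with, only two sections to reconcile.

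The conclusion rests on reading the 2.3.1 sentence as a restriction that applies in this trial. If the sponsor meant it more narrowly, the remedy changes in wording but is still needed.

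**What to change.** Add an item to 5.2, next to item 8, that names the group exactly as 2.3.1 does: subjects with a known history of anaphylaxis or anaphylactic-like reactions. Check it in the record review and the baseline history, both of which already come before the first dose. If the sponsor meant only reactions to metreleptin or its components, put that narrower wording in both 2.3.1 and 5.2.

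For participants already on drug who turn out to have such a history, use a documented individual review. Section 7.2 already provides for this through its reference to a "change in benefit-risk ratio of metreleptin treatment for an individual patient". Withdrawal should not be automatic.

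The cost is one line in 5.2, a second in 2.3.1 if the scope is narrowed, and one question in an existing history, all in a single amendment. The downside is that an occasional patient may become ineligible in a rare disease for which section 2.2 calls existing therapy inadequate. The narrower wording, if that is what was meant, would exclude fewer.
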